11.2 Missing data

Missing data is thought to be low (around 5%) but nonetheless the robustness of the findings to any patterns of missing data will be investigated using appropriate sensitivity type analyses, including multiple imputation under an assumption of missing at random.

11.3 Adjusting for centre

Due to the small sample size, adjustment by site is likely to be uninformative.

11.4 Subgroup analyses

Results will be reported by the strata created by the randomisation process (Males 65 years and older; males below 65 years; females 65 years and older; females below 65 years). Additional subgroup analysis by fall in lymphocyte (<20% fall vs \geq 20% fall), and neutrophil:lymphocyte ratio (<2.18 vs \geq 2.18) for key explanatory will be described should there be sufficient data. No formal comparisons of strata will be conducted.

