8 TRIAL PROCEDURES

8.1 Baseline assessments

All patients must have received a positive COVID-19 test result via oropharyngeal/nasopharyngeal swab (or other validated method) prior to baseline assessments being performed. [REDACTED]

[REDACTED] Other validated methodology may be used during the course of the trial e.g. saliva test, to improve the patient experience and assuming equal to or improved test validation and sensitivity.

When the patient has indicated their interest in the trial as per Section 6, the following information will be ascertained by the clinical research team member via an initial conversation (via video or phone call for community patients)*:

- Demographics – date of birth, gender.
- Height and weight.

CONFIDENTIAL

- Symptoms of COVID-19, ancillary symptoms and length of symptoms – e.g. fever ($\geq 37.8^{\circ}\text{C}$), persistent dry cough, muscle pain, shortness of breath, diarrhoea, headache, anosmia, other symptoms.
- COVID-age risk (Appendix 4)
- Other potential risk factors including smoking (pack year history), ethnicity, occupation, symptomatic household (or other) contact, other relevant medication history.
- Previous medical history – particularly chronic disease (specifically hypertension, cardiovascular disease, diabetes mellitus, hyperlipidaemia, cancer and existing respiratory conditions), history of influenza vaccination and COVID-19 vaccination (past two years).

*Alternatively, for patients recruited in a hospital setting, all baseline assessments would be performed during their attendance in the hospital, including a COVID-19 test if not previously performed.

If the above assessments are supportive of a home visit to conclude the below eligibility assessments, the patient will be asked to provide consent as per Section 9.2. The following will then be performed:

- Biochemical and haematological investigations to include:
 - Haematology – haemoglobin (Hb), white blood cells (WBC), neutrophils, lymphocytes, and platelets.
 - Biochemistry – sodium, potassium, magnesium, adjusted calcium, phosphate, urea, creatinine, total protein, albumin, bilirubin, alkaline phosphatase (ALP), alanine aminotransferase (ALT), aspartate aminotransferase (AST), clotting- prothrombin time (PT), activated partial thromboplastin time (APTT), gamma-glutamyl transferase (GGT), troponin, D-dimer.

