13 DATA ANALYSIS AND STATISTICAL CONSIDERATIONS

13.1 Description of statistical methods

All statistical aspects of the study will be fully documented in a comprehensive Statistical Analysis Plan authored by the study statistician and agreed by the independent Trial Steering Committee.

The primary outcome will be an exploration of camostat safety and toxicity, in terms of the number and severity of AEs and SAEs.

Descriptive statistics will be used to describe the demographics for each randomised group and overall. For categorical data, frequencies will be reported, and for continuous variables means and standard deviations, or for skewed data, medians and interquartile ranges will be reported.

Secondary outcomes will be reported in a similar way to the demographic data, with an estimate of the difference and standard error between the treatment groups for continuous or ordinal scale data. Medians and IQRs will be used where data are non-normally distributed. Absolute percentage difference and standard error will be reported for binary variables. Kaplan-Meier plots and life tables will be used to estimate median survival times

Subgroups will be explored where there are sufficient patients in each group. Data will be split by age (< 65 years vs ≥ 65 years), fall in lymphocyte ($<20\%$ fall vs $\geq 20\%$ fall), and neutrophil:lymphocyte ratio (<2.18 vs ≥ 2.18) for key explanatory variables.

No significance testing will be performed. Differences between treatment groups will be reported solely to inform future trials.

All enrolled patients who receive at least one dose of camostat in the treatment arm and complete Day 1 in the control arm will be evaluable for safety.

In order to be evaluable for efficacy, treatment arm patients must receive camostat for a minimum of five days, and control arm patients must either complete up to Day 14 or come off trial at an earlier timepoint due to an endpoint (e.g. hospitalisation).

Safety data will be collected from the date of written, or verbal, consent. Safety variables will be summarised by descriptive statistics.

Adverse events will be reported as tables of frequency of AEs by MedDRA system organ class and by worst severity grade observed. Tables should indicate related and unrelated events

Adverse events will be reported for each arm and presented as tables of frequency of AEs by MedDRA system organ class and by worst severity grade observed. Tables should indicate related and unrelated events.

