10 STATISTICAL METHODS SECTION FROM THE PROTOCOL

The primary outcome will be an exploration of camostat safety and toxicity, in terms of the number and severity of AEs and SAEs. Recruitment rate will be reported as numerator and denominator, with the percentage and exact binomial 95% confidence interval. The other feasibility measures will be reported in the same way.

Descriptive statistics will be used to describe the demographics for each randomised group and overall. For categorical data, frequencies will be reported, and for continuous variables means and standard deviations, or for skewed data, medians and interquartile ranges will be reported.

Secondary outcomes will be reported in a similar way to the demographic data, with an estimate of the difference and standard error between the treatment groups for continuous or ordinal scale data. Medians and IQRs will be used where data are non-normally distributed. Absolute percentage difference and standard error will be reported for binary variables. Kaplan-Meier plots and life tables will be used to estimate median survival times.

Subgroups will be explored where there are sufficient patients in each group. Data will be split by age (< 65 years vs ≥ 65 years), fall in lymphocyte (<20% fall vs $\geq 20\%$ fall), and neutrophil:lymphocyte ratio (<2.18 vs ≥ 2.18) for key explanatory variables.

No significance testing will be performed. Differences between treatment groups will be reported solely to inform future trials.

All enrolled patients who receive at least one dose of camostat in the treatment arm and complete Day 1 in the control arm will be evaluable for safety.

In order to be evaluable for efficacy, treatment arm patients must receive camostat for a minimum of five days, and control arm patients must either complete up to Day 14 or come off trial at an earlier timepoint due to an endpoint (e.g. hospitalisation).

Safety data will be collected from the date of written or verbal consent. Safety variables will be summarised by descriptive statistics.

Adverse events will be reported as tables of frequency of AEs by MedDRA system organ class and by worst severity grade observed. Tables should indicate related and unrelated events

Adverse events will be reported for each arm and presented as tables of frequency of AEs by MedDRA system organ class and by worst severity grade observed. Tables will indicate related and unrelated events

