11.1 Populations

The efficacy population will only include patients from the camostat arm where they have completed 5 days of treatment and in the control arm where they have completed 14 days of treatment or reached an endpoint (eg hospitalisation). All primary and secondary analyses will be conducted with this population. An intention-to-treat analysis of the main secondary outcomes (COVID-19 related hospital admissions, supplementary oxygen-free days, ventilator-free days, time to worst point on the 9-point ordinal scale) will also be conducted, should the data allow.

Patients who agree to the taking of blood samples will be included in the analysis of the PK data. The mean and SD will be reported at each time point (Days 7 and 14), as will the mean changes. The data may be log (or other) transformed if not normally distributed. [REDACTED]

[REDACTED] Change will be
change from previous blood test.

The safety population will include all patients with at least one dose of treatment (camostat or control). Safety data will be collected from the date of written consent. Safety variables will be summarised by descriptive statistics.

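### Lymphocyte fall is listed as a subgroup factor, but on the visible schedule it can only be measured after randomisation (minor)

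*SAP*

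**What the plan says.** Three places list the split. Protocol 13.1 introduces the subgroups with "Subgroups will be explored where there are sufficient patients in each group" and names age, fall in lymphocytes (<20% against ≥20%) and NLR (<2.18 against ≥2.18). SAP 10 repeats this as the protocol's text ("Data will be split by age" and so on). SAP 11.4 has the four age-by-sex randomisation strata and then "Additional subgroup analysis by fall in lymphocyte" and by NLR, if there are enough data. None of the three gives a reference value, a visit or a window for the fall.

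The stated weight is low. SAP 11.4 adds "No formal comparisons of strata will be conducted", and protocol 13.1 rules out significance testing. On use, protocol 13.1 says "Differences between treatment groups will be reported solely to inform future trials", and SAP 12.2 tabulates the primary safety outcomes by arm and by strata or subgroups.

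On timing, protocol 8.1 lists the baseline blood test as "Haematology – haemoglobin (Hb), white blood cells (WBC), neutrophils, lymphocytes, and platelets". Protocol 8.2 places randomisation after review of those baseline assessments. Protocol 8.3.2 schedules the next counts at Days 7 and 14.

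**The concern.** Age, sex and a screening NLR are fixed before allocation, so within each level the randomised arms remain comparable. A lymphocyte fall is different: it is part of the patient's course on camostat or on supportive care. If camostat alters that course, patients with a ≥20% fall on camostat are not the same kind of patient as those with a ≥20% fall on control. An arm difference can then appear within the subgroup with no treatment effect on the outcome.

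There are two further problems. Adverse events are recorded from consent and the efficacy time frame is Days 1 to 28, so a patient with an event before Day 7 would be classified after the outcome. Protocol 8.3.2 also allows Day 7 and Day 14 sampling to be dropped, and patients without those samples cannot be classified from trial samples.

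What is at stake is modest. Arm differences are reported to inform later trials, and nothing in the plan marks this factor as different in kind from age or NLR. A within-subgroup difference could be carried forward without that warning.

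**Working it through.** **Step 1: timing.** A percentage fall needs two counts.

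- Scheduled before randomisation: one, at screening (protocol 8.1 and 8.2).
- Scheduled after randomisation: Day 7 (±1 day) and Day 14 (protocol 8.3.2). The NLR tables in SAP 6.8 use the same three visits: Screening, Day 7, Day 14.
- Several pre-treatment values: SAP 6.2 keeps the last one as baseline and derives no pre-treatment fall.
- Routine emergency-department bloods may serve as the screening sample (protocol 9.1.2), but no second, earlier value is required. Other clinical-care results enter the analysis for the trial period (protocol 8.1).
- SAP 11.1 says "change from previous blood test" next to redacted text. It may or may not define this interval. If it does, the second count is still after randomisation.

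The earliest scheduled fall is therefore screening to Day 7.

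**Step 2: possible size of one bias route.** The documents give no effect of camostat on lymphocytes, so every model input here is an assumption; only the 50 per arm is from the plan.

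- Severity ~ N(0,1).
- Admission: logit = −2.55 + severity, which gives 10.1% in both arms. The true arm difference is 0.
- Fall = severity + N(0,1) − shift (camostat arm only). A positive shift means that camostat lessens the fall, in units of the residual SD.
- ≥20% group: fall ≥ 0.6, which is 33.6% of controls, or 50 × 0.336 = 16.8 patients, leaving 33.2 in the <20% group.
- SE = √(p₁q₁/n₁ + p₀q₀/n₀).

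Worked case, shift +0.5, for which the model puts 10.9 camostat patients in the ≥20% group and 39.1 in the <20% group:

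- ≥20%: 19.4% against 17.0%, difference +2.4 points. SE = √(0.194 × 0.806/10.9 + 0.170 × 0.830/16.8) = 15.1 points. Ratio 0.16.
- <20%: 7.5% against 6.6%, difference +0.9 points. SE = 6.0 points. Ratio 0.14.

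| Shift | <20%: camostat / control, difference (SE), ratio | ≥20%: camostat / control, difference (SE), ratio |
|---|---|---|
| 0 | 6.6 / 6.6%, 0 (6.1), 0 | 17.0 / 17.0%, 0 (13.0), 0 |
| +0.5 | 7.5 / 6.6%, +0.9 (6.0), 0.14 | 19.4 / 17.0%, +2.4 (15.1), 0.16 |
| −0.5 | 5.8 / 6.6%, −0.9 (6.3), −0.14 | 15.0 / 17.0%, −2.0 (11.7), −0.17 |
| +0.8 | 8.0 / 6.6%, +1.4 (6.0), 0.23 | 21.1 / 17.0%, +4.1 (17.0), 0.24 |
| −0.8 | 5.2 / 6.6%, −1.4 (6.4), −0.22 | 14.0 / 17.0%, −3.0 (11.3), −0.26 |

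Differences were taken before rounding.

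For a commoner outcome of the adverse-event type (logit = −0.97 + 0.7 × severity, 29.4% in both arms), the absolute ratios are 0.15 to 0.17 at shifts of ±0.5 and 0.23 to 0.27 at ±0.8.

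**Step 3: event counts.** In this model the expected admissions per arm per subgroup run from about 1.2 (22.2 × 5.2%) to 3.9 (27.8 × 14.0%). The plan's own condition of sufficient data may stop the split being reported at all.

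**The case against.** The strongest reply is that little depends on this split. It is exploratory and untested, and it appears only if the data allow. No table or listing in SAP 8.1 or 8.2 and no output in SAP 12.4 names it. All of that stands, and it sets the severity.

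A second reply is that within-split arm contrasts are inferred. SAP 11.4 breaks off at the words about key explanatory variables, and a prognostic or purely descriptive use fits the text as well. The research endpoints and the text beside the definition of change are redacted, and the schedule table is broken. This also stands: the plan permits such contrasts through the general wording of SAP 12.2 and protocol 13.1, but it does not commit to them. It does not turn a fall measured after allocation into a baseline factor.

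Third, some patients recruited in emergency departments or on wards may have earlier counts, and trial-period care bloods or the multiple imputation in SAP 11.2 could fill some gaps. That eases the missing-sample problem in part. No document defines a pre-randomisation fall from such results.

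Fourth, the calculation covers one route under assumed inputs. That is correct: the ratios do not measure the whole concern.

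A reader might infer that the trial's arm comparisons are biased as a whole. They are not affected by this split. A reader might also infer that camostat is known to change lymphocytes; the documents do not say so.

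**Conclusion.** The point holds as a minor one. On the visible schedule the lymphocyte-fall factor is formed after randomisation, and arm results within it would not be randomised comparisons. If camostat has no effect on lymphocytes, the bias by this route is zero. If it has an effect of 0.5 to 0.8 residual SD in either direction, the bias is about 0.14 to 0.27 of a standard error under the assumed models. Events before Day 7 and missing samples would add to the problem by an amount not estimated here.

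The conclusion on timing rests on the text of protocol 8.1, 8.2 and 8.3.2 and on the visits in SAP 6.8, not on the damaged schedule table. It should not be read as saying that the remaining splits give clean randomised contrasts for efficacy. SAP 11.1 says of the efficacy population "All primary and secondary analyses will be conducted with this population", and that population is itself selected after randomisation by days of treatment or follow-up.

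**What to change.** In SAP 11.4, state that subgroup comparisons between arms use pre-randomisation values only: the age-by-sex strata and the listed NLR split (<2.18 against ≥2.18), specified as the screening value. Report the proportion with a ≥20% lymphocyte fall from screening to Day 7 descriptively by arm, label it post-randomisation, and show no arm differences within the fall groups.

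SAP 10 is headed as the protocol's text, so add a note there that the SAP departs from it on this point. Align protocol 13.1 at the next amendment. It need not be amended for this alone, since protocol 15.4 says an amendment may need REC, HRA and MHRA review.

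The cost is a few lines of SAP wording and no new data, because neutrophils and lymphocytes are already taken at screening. The loss is one exploratory arm contrast. A screening value also answers a different question: it describes status at entry, not the course of the illness.

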12 LIST OF ANALYSES

Although the sample size has been calculated on recruitment rate, the primary outcome will be the comparison of adverse events and their severity between treatment arms. These will be listed overall and by strata.

12.1 Interim evaluation

At appropriate intervals, tables of results will be produced to give the Investigators the possibility to review the data and check the completeness of information collected.

This review will include:

- Feasibility of the trial to achieve the target recruitment. This will be informed by
 - Recruitment – what proportion of eligible patients consent to the trial
 - Retention – what proportion of the randomised trial patients complete the trial per protocol
 - Proportion of patients for whom the primary outcome is missing
 - Overall number of adverse events
 - Protocol deviations

[figure not shown]
No unblinded data will be made available to the investigators until the end of the trial or the DMEC decides to halt the trial.

12.2 Main study findings

The primary outcomes for this trial are safety and adverse events. These will be tabulated by treatment group and by strata/subgroups. Pregnancy, compliance, protocol deviations will also be tabulated in this way.

The majority of secondary outcomes will be reported in the main RAP. The secondary outcomes of number of oxygen-free days, ventilator-free days, and number of days to worst point on the 9-point ordinal scale (see secondary objectives in RAP for definitions) will be reported as median and range for the 28 days of follow up post-randomisation.

12.3 Transformations

12.4 Outputs

Tabular outputs have been described in the main RAP. The following analyses will be in addition to these tables.

Population: Efficacy population (at least 5 days of camostat/14 days of control)

Medians and range for the following variables will be produced by treatment group:

- Number of oxygen-free days,
- Number of ventilator-free days,
- Number of days to worst point on the 9-point ordinal scale

Kaplan-Meier plots of the following variables will be produced by treatment group:

- Time to worst point on ordinal scale

Plots of daily data will also be produced where this will aid interpretation.

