6.9 Efficacy

To evaluate efficacy of camostat by effect on COVID-19 related clinical improvement.

Time Frame: Days 1-28

Time to worst point on the scale or deterioration of two points or more (from randomisation) on a 9-point category ordinal scale.

9-point category ordinal scale:

0. Uninfected, no clinical or virological evidence of infection
1. Ambulatory, no limitation of activities
2. Ambulatory, limitation of activities
3. Hospitalised – mild disease, no oxygen therapy
4. Hospitalised – mild disease, oxygen by mask or nasal prongs
5. Hospitalised – severe disease, non-invasive ventilation or high-flow oxygen
6. Hospitalised – severe disease, intubation and mechanical ventilation
7. Hospitalised – severe disease, ventilation and additional organ support e.g. vasopressors, renal replacement therapy (RRT), extracorporeal membrane oxygenation (ECMO)
8. Death

Table 10 Ordinal Scale.

Efficacy population

Patient Number	Randomised Arm (Treatment or Control Arm)	Day 1 Scale	Worst Point on Scale	Deteriorated by more than 2 points (yes/no)	Time to worst point (Days)

Table 11: Summary Table for Secondary Endpoint Data.

Efficacy population

	All	Treatment arm	Control arm

Number of community patients admitted to hospital due to COVID-19			
Total number of patients			
Proportion of patients per arm			
Supplementary oxygen-free days at 28 days			
Number of patients			
Proportion of patients per arm			
Ventilator-free days at 28 days			
Number of patients			
Proportion of patients per arm			

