To evaluate the requirement for ventilation in patients who have received camostat as treatment for SARS-CoV-2 infection.	Ventilator-free days at 28 days (from randomisation).	
Measure Title: Number of ventilator - free days
 
Measure Description: Number of ventilator - free days
 
Time frame: Days 1-28
 
Population description: Patients who received camostat for a minimum of five days (treatment arm) or who either completed up to Day 14 or came off trial at an earlier timepoint due to an endpoint defined reason (e.g. hospitalisation).

		
Information to be presented: Median and range of ventilator free days by treatment arm (provided in Stats report).
 
Measure Title: Time to worst point on the scale or deterioration of two points or more (from randomisation) on 9 point category ordinal scale.
 
Measure Description: Median time and range to worst point on the scale or deterioration of two points or more (from randomisation) on 9 point category ordinal scale
 
Time frame: Days 1-28
 
Population description: Patients who received camostat for a minimum of five days (treatment arm) or who either completed up to Day 14 or came off trial at an earlier timepoint due to an endpoint defined reason (e.g. hospitalisation).

	
5. Hospitalised – severe disease, non-invasive ventilation or high-flow oxygen
 
6. Hospitalised – severe disease, intubation and mechanical ventilation
 
7. Hospitalised – severe disease, ventilation and additional organ support – vasopressors, renal replacement therapy (RRT), extracorporeal membrane oxygenation (ECMO)
 
8. Death
	Information to be presented: Median and range of times to worst point on the ordinal scale (provided in Stats report).
--	--	--

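### The by-arm outputs for the 9-point ordinal scale give only days to the worst point, never the worst score reached, so the endpoint cannot separate arms that worsen on the same days to different severity.

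*SAP*

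**What the plan says.** The SAP document consists of a Reporting Analysis Plan (RAP, sections 2 to 9) with the statistical analysis plan as its appendix (SAP sections 10 to 13).

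Protocol section 4, RAP 3 and RAP 6.9 define the endpoint as "Time to worst point on the scale or deterioration of two points or more (from randomisation) on a 9-point category ordinal scale", from 0 (uninfected) to 8 (death). The by-arm outputs specified for it are:

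- SAP 12.2: "number of days to worst point on the 9-point ordinal scale (see secondary objectives in RAP for definitions) will be reported as median and range", over the 28 days after randomisation.
- SAP 12.4: median and range of "Number of days to worst point on the 9-point ordinal scale", and a Kaplan-Meier plot of "Time to worst point on ordinal scale", both by treatment group in the efficacy population.
- RAP 7.4 (clinicaltrials.gov): the measure title carries the full two-part definition, but the information to be presented is "Median and range of times to worst point on the ordinal scale (provided in Stats report").
- SAP 11.1: an intention-to-treat (ITT) analysis, if the data allow, again of the time to the worst point.

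The score itself is in RAP Table 10, in the column "Worst Point on Scale". That table has one row per patient, with arm, Day 1 score, a yes/no deterioration flag and time, and no arm totals. RAP Table 11, the by-arm summary of secondary endpoints, has no ordinal-scale row. Two general statements could cover severity but name no output that does: Protocol 13.1 and SAP section 10 promise a between-arm difference and standard error for ordinal data, and SAP 12.4 allows plots of daily data where helpful.

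**The concern.** The levels of this scale carry its clinical meaning. A summary of when each patient reached their own worst level discards how bad that level was: a patient whose worst level is a mild admission and one who dies on the same day contribute the same number. Time to worst point also has no agreed good direction. A patient who is worst at entry and then recovers may have a very short time, and one who dies late has a long one.

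At stake is the use of the endpoint. The plan runs no significance tests and reports differences only to inform later trials. Planning a later trial on an ordinal endpoint needs the distribution of scores by arm, which no specified table provides.

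**Working it through.** The plan gives no figure for this endpoint. Its only design figure, the precision of the recruitment rate in Protocol 13.2, does not enter here. The check is an illustration with 50 patients per arm (the planned maximum). The event counts and days are assumptions, not figures from the documents.

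**1. Same days, different severity.** In each arm 10 patients worsen from score 2, on Days 3, 4, 5, 5, 6, 6, 7, 8, 9 and 10, and 40 never worsen. In arm A the ten die (score 8). In arm B the ten move one point, to score 3. The plan does not say what time a patient who never worsens receives, so several rules were tried. Entries are median (range) of days to worst point.

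| Rule for the 40 | Arm A | Arm B |
|---|---|---|
| Day 1 | 1 (1-10) | 1 (1-10) |
| Day 0 | 0 (0-10) | 0 (0-10) |
| Day 28 | 28 (3-28) | 28 (3-28) |

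The Kaplan-Meier curves also coincide. With censoring at Day 28, both fall to 1 - 10/50 = 0.80 at Day 10. With the Day 1 rule, both stand at 10/50 = 0.20 after Day 1 and reach 0 at Day 10. A by-arm count of worst score would show deaths 10 v 0 and score 4 or more 10 v 0, with score 3 or more 10 v 10.

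The result holds for any such rule, because the two arms have the same list of times and the score is not an input. Timing the two-point deterioration instead would not cure it: a move from 2 to 4 and a move from 2 to 8 on the same day would count alike.

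**2. Fewer deteriorations.** Here the number who worsen differs between arms, with worsening days spread in turn over Days 3 to 10. Each cell gives the arm with fewer deteriorations first.

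| Deteriorations of 50 | Median, Day 1 rule | Median, Day 28 rule | Kaplan-Meier after Day 1, Day 1 rule (k/50) | Final Kaplan-Meier, censored at Day 28 (1 - k/50) |
|---|---|---|---|---|
| 5 v 10 | 1 v 1 | 28 v 28 | 0.10 v 0.20 | 0.90 v 0.80 |
| 10 v 20 | 1 v 1 | 28 v 28 | 0.20 v 0.40 | 0.80 v 0.60 |
| 20 v 30 | 1 v 4 | 28 v 9 | 0.40 v 0.60 | 0.60 v 0.40 |
| 24 v 26 | 1 v 3 | 28 v 10 | 0.48 v 0.52 | 0.52 v 0.48 |

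Under the Day 1 rule the arm with fewer deteriorations has the lower curve and, once more than half of the other arm worsens, the earlier median. Under the Day 28 rule or censoring, the order is the expected one. When fewer than half of each arm worsens, the medians are equal under either rule.

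**The case against.** The strongest reply is that the report as a whole does show severity by arm. RAP Table 6 has a by-arm row for deaths. RAP 7.3 gives all-cause mortality and serious adverse events by arm. RAP Table 11 covers COVID-19 admissions, oxygen-free days and ventilator-free days, and SAP 12.4 adds medians for the last two. Since the scale is built from hospital admission (3 and above), oxygen (4 and above), ventilation (6 and above) and death (8), a table of worst scores overlaps these heavily. With at most 100 patients, a reader could also tally Table 10 by hand.

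Much of this stands. A reader might infer that the plan never compares severity between arms, or that a treatment turning deaths into mild admissions would show no effect. The documents do not support either. In the first illustration, Table 6 would show the deaths as 10 v 0, provided those patients are in the safety population.

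The other tables are still not a full substitute. Table 6 uses the safety population, whereas the ordinal outputs use the efficacy population. Table 11 counts admissions in community patients only. No table separates scores 3 to 7 by arm. If a patient who needs no support is credited with 28 free days (an assumption), the median free days are 28 in both arms whenever fewer than half of each arm scores below that maximum. The general promise of a difference for ordinal data, and the optional daily plots, name neither a variable nor a table that would give the score by arm.

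**Conclusion.** The point holds for the ordinal-scale outputs. Each one specified by arm is a time, so arms with the same timing and different severity give identical results on this endpoint. That conclusion rests on the list of outputs and on no assumed event rate. The size of what is hidden cannot be stated from the documents; ten deaths against ten one-point worsenings is an illustration.

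A reader might go further and conclude that the planned plot will make the better arm look harmful. That is conditional. It follows if patients who never worsen are timed at Day 1, which the plan neither states nor excludes. It does not follow if they are censored at or set to Day 28.

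The data exist and other tables cover much of the same ground, so this is an improvement to consider and not a flaw that undermines the trial's primary safety aim.

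**What to change.** Add to RAP 6.9 and SAP 12.4 a by-arm frequency table of the worst score over Days 1-28: scores 0 to 8, with cumulative rows for 3 or more, 4 or more, 6 or more, and death. Tabulate it against the Day 1 score, since patients already in hospital for other reasons may be recruited and start higher on the scale. Produce it in the efficacy and ITT populations. It needs no timing rule for patients who never worsen, because their worst score is their Day 1 score.

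Report the table beside the time-to-worst-point outputs, not in place of them. Time is the secondary endpoint in the protocol and the clinicaltrials.gov outcome, so reducing it to a listing would conflict with both.

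Before deteriorations are counted by arm, reconcile the Table 10 column "Deteriorated by more than 2 points (yes/no") with the endpoint definition, which counts a deterioration of exactly two points and which the column as worded leaves out.

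The cost is SAP and RAP wording and one extra table. The efficacy version uses variables already in Table 10; the ITT version needs the same variables for randomised patients outside that population, and Protocol 8.3 has ordinal status assessed in all patients. The downside is partial overlap with the admission, oxygen, ventilation and death summaries.
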